#### **4.4. Assessment of Compliance and Acceptability**

At baseline, week 2, week 6, week 9 and week 12 urine samples will be collected for urine nitrogen and creatinine. The ratio of nitrogen/creatinine will be used as a marker of compliance with the high protein LoBAG30 diet, as previously described (4). Subjects in both groups will complete surveys at week 1, week 6, and week 12 with questions about compliance, acceptability of the diets, and quality of life. A study investigator will contact subjects every two weeks during the diet intervention period to encourage diet compliance. Subjects will be asked to complete 3-day food diaries at the beginning, midpoint, and end of the 12 week study. If funding is available, an unannounced 24-hour diet recall will be conducted via telephone by the Nutrition Coordinating Center at the University of Minnesota. The recall will be administered by a trained interviewer and analyzed using Nutrition Data System for Research software.

#### **4.5. Subject Compensation**

Subjects will be provided a total stipend of \$600 for completion of the study. This amount includes a weekly stipend to partially account for the increased price of required foods (\$15 per week), compensation for time (average \$15 per week), and a bonus for study completion (\$240). Payments will be made at regular intervals during the study. If a subject withdraws from the study before completion, compensation will be provided for each week of participation up to the time of withdrawal. In addition to the above compensation, parking will be paid for at study visits.

Subjects who come for a screening visit only (do not qualify to go forward with the study) will be mailed a check with compensation (\$30). Subjects who enroll in the study will be given the option of payment using pre-paid debit cards with the Greenphire ClinCard system. If a subject chooses this option, they will be given a handout with instruction on use of the card. If a subject prefers not to use this option, they will be paid through checks mailed following study visits. The payment schedule will be the same with either reimbursement option, except that check processing may delay reimbursement by a few weeks.

#### **4.6 Data Collection**

Data will be collected by study investigators in source documents and will be entered into a RedCap database. Data will be identified using indirect identifiers. Hard copies of source documents will be stored in a locked office. All computers used for this study will be password protected. In addition the

RedCap database will be password protected and will only be accessible to those study investigators and staff who require access.

Blood, urine, and stool specimens will be collected by the study investigators or Clinical and Translational Science Institute (CTSI) or Clinical Research Unit (CRU) staff. All specimens will be identified using indirect identifiers and appropriate numbering and labeling for date, visit number, and time of collection. Specimens will be either transported directly to the lab for processing or will be stored in CTSI freezers.

The study PI will manage the study data and specimens, with assistance from the study coordinator. Records and frozen specimens will be stored indefinitely.

Protected health information will not be saved for potential participants who are screened but do not come in for a study visit and thus do not give signed informed consent. At the conclusion of the screening survey potential participants will be asked if they are willing to be contacted about future studies for which they may be eligible. If yes, their name, age at time of screen, gender, reason for study ineligibility, method of finding out about the study (flier, letter, etc), and contact information will be saved in a password protected log. All other protected health information collected during the screening survey will be destroyed.

Following study enrollment all study participants will have a M Health medical record number (MRN) identified or created. The electronic health record (EPIC) may be accessed and used for scheduling purposes, as required by the clinical research unit (CRU).

#### **4.7. Methods of Data Analysis**

The primary outcome will be HgbA1c at the end of the 12-week study period. Results will be compared pre and post diet intervention (within an individual subject) using paired t-tests and between dietary interventions (LoBAG30 versus control) using unpaired t-tests. Data will be analyzed at study completion.

Sample size was estimated a priori based on a two-tailed type I error of 0.05. For a difference of 1.5 points in HgbA1c and a power of 80%, 12 participants are required per intervention group. This number was increased by 30% to account for participant loss during screening, and an additional 30% to account for participant attrition, yielding 19 participants per intervention group (total 38 participants). An additional 12 participants have been enrolled using pilot funding from the University of Minnesota (of which 8 were eligible and 6 completed the entire study intervention).

This estimate uses preliminary data from existing LoBAG30 studies which were collected in a carefully controlled research setting. This differs from the conditions planned for this study. There are no data on the performance of the LoBAG30 diet in a free-living population of subjects with DM2. Thus, we will generate data that can be used to estimate effect size and variability for a power calculation for a future larger clinical trial.

With a goal of 38 plus 6 subjects completing the entire 12-week intervention, we anticipate recruiting up to 70 subjects in total.

If a subject withdraws from the study prior to study completion they will be invited to complete the final study visit prior to withdrawal, if possible. Any data collected from the subject prior to study withdrawal will be included in the final analysis. In the case of subject withdrawal an additional subject will be recruited to replace accordingly, dependent on funding.

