## Project Summary

Diet is a cornerstone of type 2 diabetes mellitus (DM2) treatment. Current standard of care diet recommendations focus on caloric restriction and weight loss, goals which can be difficult for patients to achieve. A moderate carbohydrate, high protein diet has been designed specifically for people with DM2, and has shown promising results in preliminary studies. This diet, called the Low Biologically Available Glucose (LoBAG) Diet, does not require caloric restriction or weight loss to produce beneficial effects. Preliminary data are exciting but studies were done only in a small subject population and in a carefully controlled research setting that was not typical of life in the real world. The purpose of this project is to expand upon the preliminary studies and offer the LoBAG diet to a free-living population of people with DM2. In addition, as part of this project, we propose a pilot study to assess the changes in the gut microbiome that occur with this diet in people with DM2.

Subjects with DM2 will be enrolled in a randomized, parallel group trial of the LoBAG diet or a control diet over a 12 week intervention period. The subjects will be free-living and will do food preparation on their own. The main intervention will be instruction in either the LoBAG diet or the control diet. Measures of glycemic control will be collected before, during, and after the diet intervention. Stool samples will be used to collect preliminary data on gut microbiome changes. The diets will be isocaloric and subjects will not be asked to lose weight during the study. Our specific aims include: 1) to determine if the LoBAG diet improves hemoglobin A1c (HgbA1c) in a free-living population with DM2, 2) to investigate the effects of the LoBAG diet on fasting and postprandial glucose and insulin, fructosamine, and lipids, and 3) to determine the effects of the LoBAG diet on the composition of the gut microbiome. The hypothesis to be tested is that the LoBAG diet will produce a significant reduction in HgbA1c when compared to the control diet. The significance of this project will be to expand the generalizability of the LoBAG diet to a free-living population and to potentially improve dietary recommendations for the treatment and control of DM2.

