### **2. Hypotheses**

We hypothesize that the LoBAG30 diet will produce a greater reduction in HgbA1c over 12 weeks in a free-living population of subjects with DM2 than a control diet consistent with ADA guidelines, without the need for weight loss. We have an additional exploratory hypothesis that the LoBAG30 diet will induce potential beneficial changes in the gut microbiome, including increased species diversity, increased relative abundance of species associated with a healthy microbiome profile, and increases in short chain fatty acids and secondary bile acids.

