#### **4.2. Outcome Measures**

The primary endpoint will be HgbA1c at the end of the 12 week diet intervention period. Secondary endpoints will be:

- 1) Weight
- 2) Fasting plasma glucose
- 3) Fasting serum insulin
- 4) Postprandial glucose response at +30, +60, +90, +120, +180 and +240 minutes following the start of a meal consistent with the assigned diet
- 5) Postprandial insulin response at +30, +60, +90, +120, +180 and +240 minutes following the start of a meal consistent with the assigned diet
- 6) Fructosamine
- 7) Fasting serum lipids
- 8) Stool samples for microbiome species analysis. Samples will also be saved for possible bacterial metabolite analysis.
- 9) Glucose variability as measured by continuous glucose monitoring (CGM).

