## Appendix 1: Timeline and Details of Study Visits

**Screen.** No visit needed. Will usually be done by telephone; may also be done by email or in person. (20 minutes)

**Visit 1.** Consent and Screening Visit. (1 hour)

- Review consent document and obtain informed consent.
- Collect baseline compliance survey, Diet Satisfaction Questionnaire, and Diabetes Treatment Satisfaction Questionnaire. Can alternatively be collected at visit 2.
- Measure weight and height.
- Non-fasting blood draw (for HgbA1c, basic metabolic panel, and complete blood count)
- Collect urine sample (for baseline urine nitrogen and urine creatinine, urine microalbumin, and pregnancy test if female and premenopausal).
- Send home with 3-day food intake diary (to be used by the study dietitian for caloric planning; the same food diary will also be collected at visit 4 and visit 6).
- If funding allows, place Abbott Freestyle Libre CGM. Provide supplies to return the CGM sensor (by mail or in person).
- Provide stool collection kit. Give instruction in stool sample collection.

Details for stool sample collection:

- Subject self-collects at home by sampling a stool with a sterile swab and putting the sample in a collection tube containing a preservative.
- This room-temperature-stable sample can be delivered to study investigators by the subject at study visits, or can be returned through the mail.
- Study staff will put the de-identified sample into the CTSI storage freezer.

**Randomization.** No visit needed.

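### Section 4.7 gives week-12 HgbA1c both within-arm paired tests and an unadjusted between-arm test, does not say which decides the trial, and leaves baseline HgbA1c and the strata out of the comparison

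*Combined protocol and SAP*

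**What the plan says.** Section 4.2 defines the endpoint: "The primary endpoint will be HgbA1c at the end of the 12 week diet intervention period". Section 4.7, the only analysis section, states: "Results will be compared pre and post diet intervention (within an individual subject) using paired t-tests and between dietary interventions", the latter being LoBAG30 "versus control) using unpaired t-tests". It names no primary test, gives no order or multiplicity rule, and does not say whether the unpaired test uses the final value or the change. It mentions no covariates. The two-sided 0.05 level appears only in the sample-size paragraph.

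The question itself is stated as a comparison of arms. The Project Summary says: "The hypothesis to be tested is that the LoBAG diet will produce a significant reduction in HgbA1c when compared to the control diet". Section 2 says the LoBAG30 "diet will produce a greater reduction in HgbA1c over 12 weeks in a free-living population of subjects with DM2 than a control diet", and Section 3.1 compares the reduction under the two diets. Only the short form of aim 1 in the Project Summary has no comparator: "to determine if the LoBAG diet improves hemoglobin A1c (HgbA1c) in a free-living population with DM2".

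Section 4.3 stratifies randomisation by diabetes treatment and by HgbA1c. Baseline HgbA1c comes from Visit 1, before randomisation (Appendix 1: "Non-fasting blood draw (for HgbA1c, basic metabolic panel, and complete blood count").

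**The concern.** Paired and unpaired tests answer different questions and can disagree. The paired test asks whether HgbA1c changed in one arm, whatever the cause. Both arms receive individual dietitian instruction, reinforcement at weeks 2, 6 and 9 (Section 4.3), and investigator contact every two weeks (Section 4.4), so some fall common to both arms is plausible. A significant LoBAG fall beside a non-significant control fall would then say little about the diet.

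The contrast is a natural one to draw. Section 1.1 summarises the earlier LoBAG20 crossover trial in this way: a significant fall on the test diet and no significant change on control, with no between-diet p-value given. In a small trial the same pattern can easily arise by chance. Section 4.7 also says the data will inform the effect size for a larger trial. A within-arm fall would overstate that effect if both arms improve.

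A second, smaller cost is precision. The planned comparison ignores a pre-randomisation baseline that is already collected and strata that are already used.

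**Working it through.** **Inputs from the documents.** 44 completers (Section 4.1) at 1:1 gives 44 / 2 = 22 per arm. The test level is two-sided 0.05 (Section 4.7).

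**Assumed inputs.** The documents give neither an SD of change nor an expected common fall. I take SD 0.8 to 1.0 and vary the fall. The plan's own figure of 12 per group for a 1.5-point difference at 80% power cannot be reproduced, because no SD is stated. Solving the unpaired t-test backwards gives an SD of about 1.25, which I use as a sensitivity value.

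**Step 1: chance that only LoBAG is significant when the true fall is equal.** Let *p* be the probability that one arm's paired test is significant in the direction of a fall. It comes from the noncentral t distribution with 21 degrees of freedom and noncentrality fall / (SD / √22). The arms are independent, so the chance that LoBAG is significant and control is not is *p*(1 − *p*). This cannot exceed 0.25, reached at *p* = 0.5.

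Example: fall 0.4, SD 1.0. Noncentrality = 0.4 × √22 = 1.88, *p* = 0.433, *p*(1 − *p*) = 0.245.

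| Equal fall (points) | SD 0.8: *p* | only LoBAG significant | SD 1.0: *p* | only LoBAG significant |
|---|---|---|---|---|
| 0 | 0.025 | 2.4% | 0.025 | 2.4% |
| 0.1 | 0.081 | 7.4% | 0.065 | 6.1% |
| 0.3 | 0.389 | 23.8% | 0.269 | 19.6% |
| 0.4 | 0.609 | 23.8% | 0.433 | 24.5% |
| 0.5 | 0.798 | 16.1% | 0.609 | 23.8% |
| 0.7 | 0.974 | 2.5% | 0.879 | 10.6% |
| 0.9 | 0.999 | 0.1% | 0.980 | 1.9% |

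(Percentages use unrounded *p*.) At SD 1.25, falls of 0.3 and 0.4 give 15.3% and 21.0%.

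**Step 2: the between-arm test.** In 200,000 simulated trials per setting with equal falls of 0 to 0.7, the unpaired test rejected in 4.9 to 5.1%, about half of these favouring LoBAG. A common fall cancels in the difference between arms.

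**Step 3: what baseline adjustment buys.** With variance σ² at both times and baseline-to-final correlation ρ (assumed 0.5 to 0.7), the residual variances are:
- final-value t-test: σ²
- change-score t-test: 2σ²(1 − ρ)
- ANCOVA: σ²(1 − ρ²)

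ANCOVA relative to the final-value test is 1 − ρ²: 1 − 0.25 = 0.75 at ρ = 0.5, and 1 − 0.49 = 0.51 at ρ = 0.7. Relative to the change-score test it is (1 + ρ)/2: 0.75 and 0.85. The gain therefore depends on which unpaired test Section 4.7 means.

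**The case against.** The strongest reply is that the documents already settle the question. The Project Summary, Section 2 and Section 3.1 all state a comparison with control, and the sample size is set per intervention group. This stands. A reader might infer that the plan lets an equal fall in both arms be reported as a LoBAG effect. The documents do not support that: nothing in them lets a within-arm result count as success, and such a report would contradict the stated hypothesis. The order in which Section 4.7 lists the tests is not a hierarchy either. What remains is that a hypothesis is not a decision rule, and the section that should supply one does not.

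A reader might also infer that contrasting the two paired tests misleads far more than 5% of the time whenever both arms improve equally. The table shows otherwise: the rate is high only for intermediate falls.

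The unpaired t-test is valid under randomisation, so ANCOVA improves precision and does not repair a bias. That also stands. Within-arm changes are useful for planning the later trial; means with confidence intervals serve that purpose without a test.

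Finally, one might extend baseline adjustment to every continuous endpoint. That fails for postprandial glucose and insulin. Their Visit 2 values are measured after randomisation, following a meal of the assigned composition (Appendix 1), so they may already carry an effect of the arm.

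**Conclusion.** The point holds as a gap between a clear between-arm hypothesis and an analysis section that does not turn it into one named, baseline-adjusted primary test. At worst, for an equal fall of 0.3 to 0.4 points with 22 per arm and SD 0.8 to 1.0, about one trial in four or five would show a significant fall on LoBAG only, with no true difference between diets. Those SDs and falls, and the correlations behind the precision gain, are assumptions. It should be corrected, but it does not invalidate the trial, because the right comparison is already planned and only needs to be designated.

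**What to change.** In Section 4.7:

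- Make the between-arm difference in week-12 HgbA1c the single primary test at two-sided 0.05. Estimate it by ANCOVA with baseline (Visit 1) HgbA1c, diabetes treatment and the HgbA1c stratum as covariates, and report the 95% confidence interval.
- Report within-arm changes as descriptive means with 95% confidence intervals, and draw no efficacy conclusion from them.
- Use the same approach for fasting endpoints whose baseline is drawn before the test meal and the start of the diet. Do not adjust postprandial glucose or insulin for the Visit 2 meal response.

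The cost is wording. No new data, visits or participants are needed. Three covariates use three degrees of freedom (44 − 2 = 42 becomes 44 − 5 = 39). The downside is that the within-arm p-values lose their inferential role.

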#### **4.3. Intervention**

A randomized, controlled, parallel group design will be used to compare the effects of the LoBAG30 diet or a balanced diet consistent with current ADA guidelines on our outcomes. Dietary intervention periods will be 12 weeks long. Both the LoBAG and control diets will consist of common foods.

Subjects will be asked to keep their physical activity level constant during the study. Medications for diabetes will be continued without change during the study. Medications will be monitored, and if a participant's medications are altered this will be noted. If antibiotics are used during the study this will be recorded. Subjects will be instructed that they do not need to monitor blood sugars regularly at home.

After enrollment and consent subjects will be randomized in a 1:1 allocation ratio to the LoBAG30 diet or a balanced diet consistent with ADA guidelines. Randomization will be stratified by diabetes treatment at enrollment (no glycemic medications or metformin) and by HgbA1c (7.0-8.5% or 8.5-9.5%), and implemented within stratum using randomly permuted block sizes of 2 and 4. If closely related subjects choose to enroll together (for example spouses or subjects that live together, and would typically share meals) they will be randomized to the same study arm. Baseline measures will be collected. Subjects will meet individually with the study dietitian, who will provide diet instruction, sample menus, and recipes consistent with the assigned diet. Dietitian consultation may be conducted

in person or by phone. During week 2 subjects will have a repeat consult with the dietitian to reinforce diet instruction. If weight has changed caloric intake will be adjusted as necessary for a goal of weight stability. A midpoint visit will be conducted at week 6, during which subjects will provide a blood sample, urine sample, and a stool sample, and will consult with the dietitian for reinforcement of diet advice. If weight has changed caloric intake will be adjusted to prevent further change. Midpoint blood and stool samples will be stored and analyzed in the future based on available funding. At week 9 subjects will consult with the study dietitian for reinforcement of diet advice and collection of a urine sample to assess compliance. The final study visit will be at the end of week 12. All outcome measures will be assessed at the final visit.

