#### **4.9. Anticipated Problems and Proposed Solutions**

Although a free-living study cohort was purposefully chosen to answer the central question of this study, it is anticipated that compliance with study diets in this cohort will be lower than that in previous LoBAG diet studies. To address this, measures of compliance have been included, and frequent phone calls added to the protocol to encourage diet compliance. Although the dietary interventions in this study are meant to be weight stable, we acknowledge that weight change during the study may influence our results. For this reason, we have included three predetermined points in the protocol when caloric advice can be adjusted if indicated. Finally, use of medications for diabetes could impact the size of the effect of the LoBAG30 diet on HgbA1c, and so we have limited inclusion criteria to no glycemic medication or metformin only. We will also use stratified randomization to ensure equal distribution of medication use across study groups.

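### The between-arm test of HgbA1c in Section 4.7 is an unadjusted t-test, although baseline HgbA1c and diabetes treatment are known before randomisation and stratify it

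*Combined protocol and SAP*

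**What the plan says.** Section 4.2 sets the endpoint: "The primary endpoint will be HgbA1c at the end of the 12 week diet intervention period". Section 4.7 repeats it and gives two kinds of test: paired t-tests within a subject, and a comparison of LoBAG30 "versus control) using unpaired t-tests". Only the second compares the diets. No covariate, stratified analysis or model appears anywhere.

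Section 4.3 stratifies randomisation by diabetes treatment at enrolment (none or metformin) and by two HgbA1c bands that meet at 8.5%. Section 4.1 makes both factors eligibility criteria, and Appendix 1 places the HgbA1c draw at Visit 1, before randomisation. Section 4.9 gives the reason for stratifying on treatment: "We will also use stratified randomization to ensure equal distribution of medication use across study groups".

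The hypothesis in Section 2 is worded differently from the endpoint. It says the LoBAG30 diet "will produce a greater reduction in HgbA1c over 12 weeks in a free-living population of subjects with DM2", and Aim 1 in Section 3.1 also speaks of a reduction.

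**The concern.** Stratifying balances the arms on the two factors and so removes some chance variation from the arm difference. An unadjusted t-test leaves that variation in its standard error. If the factors predict week-12 HgbA1c, the confidence interval is wider than the design warrants and the test rejects too rarely under the null. This is lost precision, not bias.

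The plan itself gives two reasons to care. Section 4.7 says there are no free-living data on this diet and that "we will generate data that can be used to estimate effect size and variability for a power calculation for a future larger clinical trial", so the width of the estimate matters whatever the power. Section 4.9 says "it is anticipated that compliance with study diets in this cohort will be lower than that in previous LoBAG diet studies", so an effect below the planned 1.5 points is a realistic prospect.

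**Working it through.** **Inputs from the documents.** Two-sided alpha 0.05, 80% power, a 1.5-point difference and 12 per group (4.7); 44 completers (4.1), taken as 22 per arm under 1:1 allocation (4.3); HgbA1c 7.0-9.5% at entry (4.1).

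**Not in the documents, so assumed.** The SD; the correlation r between Visit 1 and week-12 HgbA1c; a baseline uniform on 7.0-9.5%; half the subjects on metformin.

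**1. The plan's figure.** With no SD stated, 12 per group cannot be reproduced independently, but it can be solved backwards. With the noncentral t, 12 per group at 80% power needs a standardised difference of 1.197, so SD = 1.5 / 1.197 = 1.253. This is first taken as the SD of the week-12 value.

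**2. Power of the unadjusted test at 22 per arm (42 df).** SE = 1.253 × √(2/22) = 0.378. Power is 97.2% at 1.5 points and 73.4% at 1.0 point.

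**3. Plausible range of r.** The baseline SD is 2.5/√12 = 0.722. If the slope of week-12 on baseline HgbA1c is at most 1, r is at most 0.722/1.253 = 0.58.

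**4. What adjustment does.** The residual SD becomes about 1.253 × √(1 − r²). At r = 0.5 this is 1.085, so SE = 1.085 × √(2/22) = 0.327. With 40 df (t = 2.021) the half-width is 0.66.

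**5. Simulation under the planned randomisation.** 20,000 trials per row, four strata, permuted blocks of 2 and 4, true difference 1.0 point, treatment not prognostic. The adjusted model contains Visit 1 HgbA1c and diabetes treatment.

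| r | Power: t-test, week 12 | Power: t-test, change | Power: adjusted | 95% CI half-width: week-12 t-test | 95% CI half-width: adjusted | Type I error: week-12 t-test |
|---|---|---|---|---|---|---|
| 0 | 72.7% | 60.8% | 72.1% | 0.76 | 0.76 | 4.9% |
| 0.2 | 73.2% | 69.3% | 74.1% | 0.76 | 0.75 | 4.6% |
| 0.3 | 74.4% | 74.8% | 77.3% | 0.76 | 0.73 | 4.2% |
| 0.5 | 74.9% | 84.6% | 84.4% | 0.76 | 0.66 | 3.3% |
| 0.58 | 76.0% | 88.7% | 88.4% | 0.76 | 0.62 | 2.7% |

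The adjusted model's type I error is 4.9-5.0% throughout. The reason for the conservatism shows at r = 0.5: the week-12 difference varies with an SE of 0.348, while the t-test reports 0.380.

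**6. If 1.253 is instead the SD of the change.** Treatment again not prognostic, true difference 1.0 point.

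| Slope | Power: t-test, week 12 | Power: t-test, change | Power: adjusted |
|---|---|---|---|
| 0.5 | 74.3% | 74.3% | 76.7% |
| 0.75 | 67.5% | 73.6% | 73.9% |
| 1 | 62.0% | 73.4% | 73.1% |

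**7. If treatment also predicts week-12 HgbA1c.** With an assumed 0.5-point effect and the total SD unchanged, power goes from 74.4% to 78.5% (r = 0.3) and from 74.8% to 85.9% (r = 0.5). With 1.0 point it goes from 75.9% to 84.5% and from 77.4% to 91.6%.

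**8. Final value or change.** With Visit 1 HgbA1c in the model, the arm coefficient and its SE are the same for either outcome. The simulated values agreed to within 1e-13.

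**The case against.** The strongest objection concerns size. Section 4.7 does not say whether the between-arm t-test uses the week-12 value or the change, and the hypothesis and Aim 1 both speak of a reduction. A test on the change does use Visit 1 HgbA1c. The implied SD may also belong to the change. Section 1.1 reports five-week falls in the two earlier LoBAG30 studies of 10.8 − 9.1 = 1.7 and 10.0 − 8.7 = 1.3 points, which average 1.5, exactly the planned difference. On that reading, adjustment beats the change t-test by 2.4 points at most and is level with it at slopes of 0.75 and 1.

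This stands as a limit on the gain. It does not rescue the text: 4.2 and 4.7 define the outcome as the week-12 value, and no change score is defined. Even with 1.253 as the SD of the change, the week-12 t-test loses 2.4, 6.4 and 11.1 points to the adjusted model. With 1.253 as the week-12 SD, the change t-test loses 11 points at r = 0. Neither t-test is safe across the range. The adjusted model is never more than 0.6 points below the better one.

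It is also fair that nothing in the documents supports a prognostic treatment effect of 0.5 or 1.0 point. Section 4.9 speaks of medication altering the size of the diet effect, which an additive term does not model. Step 7 is illustration only, and the conclusion does not rest on it.

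**Conclusion.** The concern holds. The planned test is valid but inefficient, and it does not use the factors on which the design stratifies. That the covariates are missing is certain from the text. The size of the loss is not, because SD and r are assumed.

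Against the week-12 t-test, with 1.253 as the week-12 SD and treatment not prognostic, the gain at 1.0 point is negligible for r of 0.2 or less, about 3 power points at r = 0.3, and 9 to 12 points at r of 0.5 to 0.58. Against a t-test on the change, it is about 11 points at r = 0, about 3 at r = 0.3 and nil at r = 0.5. At the planned 1.5 points little is at stake. The change should be made because it is nearly free, narrows the estimate wherever baseline is prognostic, and settles which between-arm comparison is primary.

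**What to change.** In 4.7, state for HgbA1c:

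> The single primary between-arm analysis is a linear model of week-12 HgbA1c on diet arm, Visit 1 HgbA1c (continuous) and diabetes treatment at enrollment (none or metformin). The arm coefficient is reported with its 95% CI and two-sided p-value.

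The paired within-subject comparisons can stay. Using HgbA1c as a continuous covariate also avoids deciding in the analysis which band a value of 8.5% belongs to. Since 4.7 wants variability for a later trial, it would help to report as well the residual SD, the week-12 SD by arm and the correlation between Visit 1 and week-12 HgbA1c.

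The cost is wording and two degrees of freedom (42 to 40). If neither factor is prognostic, power at 1.0 point falls by about 0.6 points (72.7% to 72.1%). No new data are needed.

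The change does not deal with household members assigned to the same arm (4.3) or subjects without a week-12 value (4.7). Both affect the t-test equally and need their own rule.
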